4 STUDY DESIGN

4.1 Description and Justification of Study Design

I. Cluster-Randomized Controlled Trial

The study is a cluster randomized controlled trial. The cluster-randomized controlled trial design¹⁴² is most appropriate to our goal of improving health care systems—that is, routine dialysis care. A cluster-randomized controlled trial design is needed because the interventions are, by nature, facility-level strategies. For example, team-based provider education and checklist implementation are geared towards all care team members in hemodialysis facilities. Similarly, peer mentoring is ultimately meant to be offered to a randomly-selected group of patients within a hemodialysis facility. See attached Script for UM Study Coordinator to use when calling patients to offer them Peer Mentoring.

Furthermore, a cluster-randomized controlled trial design is most appropriate for optimizing pragmatic trial designs, of which our trial is an example.¹⁴³ Finally, a cluster-randomized controlled trial design minimizes the potential problem of contamination.¹⁴⁴ We considered contamination likely given the nature of the interventions: it would be difficult for trained providers who are accustomed to using checklists to change their practice patterns depending on the patient to whom they are providing care. Moreover, peer mentoring will be given to patients based on their home facility. Because hemodialysis is typically administered in a shared location, patients might learn about others' peer mentoring interactions through conversation, which could be seen as a design problem. Accordingly, individual patients not randomized to receive peer mentoring could indirectly receive aspects of it through changes in other patients' attitudes and/or behavior. However, this effect could actually become an advantage within a cluster-randomized controlled trial, because patients who do not directly receive the intervention could nonetheless benefit from it via passive exposure.

II. Factorial Design

Our 2X2 factorial design trial is a comparative effectiveness trial that is uniquely positioned to answer multiple treatment comparison questions (see below), including “*What is the comparative effectiveness of patient mentoring versus provider education?*”

This design is a *superior choice* in our circumstance to a simple two-arm trial design (i.e., provider education vs. patient activation intervention only) because it provides a control group for testing each intervention. An aim of the project is to translate effective interventions from other settings into the setting of outpatient hemodialysis care. Therefore, there is an inherent need to validate the effectiveness of both interventions in this new environment and patient population (see treatment comparison questions i and ii below), while also comparing their relative magnitudes of effect (see treatment comparison question iii below) and their potentially synergistic or antagonistic effects (see treatment comparison question iv below). If we were to conduct a simple two-arm trial (provider education vs. patient activation only), we would only be able to answer treatment comparison question iii below.

Table 1 - 2 by 2 Factorial Design with Facility and Patient Sample Sizes - # Facilities (# Patients)			
	Patient Activation Intervention		Total
Provider Education	Yes (N_2)	No	
Yes (N_1)	A - 5 (300)	B - 5 (300)	10 (600)
No	C - 5 (300)	D - 5 (300)	10 (600)
Total	10 (600)	10 (600)	20 (1,200)

Therefore, we have designed a trial to answer the following **four treatment comparison questions (see Table 1):**

- i. Provider education vs. no provider education (assumes no interaction between interventions)
 - a. Cells ((A+B) vs. (C+D)) – F test comparison
- ii. Peer mentoring vs. no peer mentoring (assumes no interaction between interventions)
 - a. Cells ((A+C) vs. (B+D)) – F test comparison

Note that all data are re-used in the comparisons for i and ii. This shows a key advantage of the 2x2 design: it allows testing two interventions for the “price of one”. Furthermore, if an interaction is seen (question iv below), then the effect of one intervention can be estimated at each level of the other intervention.

- iii. Comparative effectiveness of provider education alone vs. peer mentoring alone
 - a. Cell B vs. C – F test comparison. The head-to-head comparison of the magnitude of effect for the two interventions is **actually comparing only the interventions alone, in the absence of the other ones.**

One problem with limiting the focus of this trial to only this comparison (as in a simple two-arm trial) is that if the two interventions were found to be equally effective, there would be no way to determine whether either represented an improvement over standard care. Without a control group, changes in the intervention groups compared to baseline could be attributed to secular trends. Because we have a control group in our design, we can rule out (or confirm) secular trends; therefore, when paired with tests i and ii above, we are able to determine simultaneously that one intervention is both: 1) better (or not) than standard care, and 2) equivalent (or not) to the other intervention.

- iv. Are there synergistic or antagonistic effects between the provider education and peer mentoring interventions?
 - a. The purpose of this test is to determine whether the effect of one intervention differs depending on the presence of the other intervention. The test compares:
 - [Cells ((A-C) – (B-D))] – F test comparison to examine the effects of provider education intervention with and without the presence of the patient activation intervention.
 - This is equivalent to ((A-B) – (C-D)), which examines the patient activation intervention with or without provider education.

This interaction test will provide power to detect strong synergistic or antagonistic effects.

The use of factorial designs in clinical trials is widely accepted, and is discussed, for example, in a well-known book on clinical trials.¹⁴⁵ Two particular advantages of factorial designs mentioned in this book are the **gain in efficiency** (the ability to test two treatments using the same number of subjects ordinarily used to test a single treatment) and the **ability to test for interaction** between treatments. This statistically efficient approach is valuable for health care interventions, where rigorous evaluation is typically expensive.¹⁴⁶

One wrinkle in the analysis of factorial designs is that interaction effects must be assumed to be null in order to test the main effects, but interaction effects are often of interest and are generally tested. Much has been written about this issue in the statistical literature; in practice, main effects are presented in the absence of a (statistically or clinically) significant interaction. When a statistically and clinically significant interaction is present, then the effect of each intervention is presented in the presence and absence of the other. Note that no other design can even test the presence of an interaction, so the simplicity gained by other analyses is at the cost of ignoring the possibility of interaction.

After the 12-week baseline period we plan to track outcomes for 36 weeks (24-week intervention period and 12-week post-intervention period). The parallel design with a 24-week intervention period, in assessing a post-intervention follow-up period, will generate valuable information related to the extent to which the intervention can sustain effects beyond an intensive implementation period. This meets the need for longer-term effectiveness studies of patient safety checklists.¹⁴⁷ This will also help clinics to understand an optimal schedule for intervention implementation.

III. Trial phase

The study is designed to be a cluster-randomized, pragmatic comparative effectiveness trial. As such, the trial will take place as part of routine HD care, with low-intensity patient follow-up and use of outcome data already gathered routinely by facilities.¹¹⁸ As such, this trial leverages unobtrusive existing electronic health record data to collect data regarding outcomes with the addition of two new data collection items to be collected through the electronic health record.¹⁴⁸

IV. Multi-center trial

The study will take place in 20 outpatient hemodialysis facilities operated by FMCNA. FMCNA has provided one site Principal Investigator for the complete study, since all sites are part of the same organization. All data from each of these facilities will be provided by FMCNA through its central corporate data warehouse, which aggregates data across FMCNA's digital documentation system. FMCNA will submit an IRB Authorization Agreement to cede IRB review and oversight to the University of Michigan.

V. Study Arms

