5.4 TREATMENT ASSIGNMENT PROCEDURES

5.4.1 Randomization Procedures

The 20 hemodialysis facilities will be randomized to the four intervention combinations of the 2x2 factorial design, assigning 5 facilities to each of the 4 combinations (both provider education and patient activation using peer mentoring; provider education alone; patient activation alone; and neither intervention). Facilities will be stratified by geographic region and socio-economic status to ensure treatment balance on those factors.

With regard to peer mentoring only, we will randomly select patients who are not vulnerable and have not opted out of the study in succession, until approximately 30 English-speaking patients in a facility accept peer mentoring. Patient randomization will be stratified by treatment shift. Every time a patient declines to participate, we will choose another patient randomly until the enrollment target is reached. Patients entering a facility randomized to the patient activation intervention during weeks 1-18 of the 24-week intervention period will be added to the list of patients eligible for peer mentoring from which patients are randomly selected for peer mentoring. We anticipate that 15-20% of patients in the study facilities will be replaced by new patients during the 11-month study period due to mortality, change in ESRD treatment modality (e.g., a kidney transplant), or changing facilities.

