11 STATISTICAL CONSIDERATIONS

11.1 STUDY HYPOTHESES

We will compare two interventions to improve the cardiovascular/hemodynamic stability of hemodialysis care by pursuing the following specific aims:

- **Aim 1** Conduct a cluster-randomized controlled trial (CRCT) to test and compare the effects of the above HD facility-level interventions on the primary outcome of dialysis session stability over an intervention period of 24 weeks and a post-intervention follow-up period of 12 weeks.
- **Aim 2** Test and compare the effects of the two HD facility-level interventions on secondary patient-centered clinical outcomes, including: patient symptoms, fluid adherence, dialysis adherence, quality of life, hospitalizations and mortality over the same timeframe.
- **Aim 3** Identify factors associated with successful implementation of the interventions, and ways in which implementation may influence intervention effectiveness.

Our main study hypothesis is that hemodialysis session stability will significantly improve with either multimodal provider education or patient activation interventions, and that multimodal provider education will show a larger improvement. This hypothesis is based on our expectation that some hemodialysis patients might refuse or be unable to participate in peer mentoring, potentially leading to greater penetration of the provider intervention. We will test this main hypothesis and explore this potential explanation of any differential improvement as part of our planned sensitivity, mediation and moderation analyses.

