11.2 SAMPLE SIZE CONSIDERATIONS

I. Primary Outcome

For Aim 1, the outcome is a dichotomous measure of HD stability, where an unstable session is defined as the dialysis session stability, where an unstable session is defined as SBP falling below 100 when the starting SBP was ≥ 100 . This outcome will be collected through digital records for all HD sessions of all patients at each facility during the study period. The analysis will be done in two ways. First, as a continuous variable, as described in the power analysis. Using individuals with a minimum of 60 dialysis sessions, the proportion of unstable sessions will be computed. Linear mixed models will be employed to compare individuals in facilities in the two treatment arms to individuals in the non-intervention facilities. Random effects for facility clustering will be accounted for using the MIXED procedure in SAS. As a sensitivity analysis, dialysis session stability will also be examined as a yes/no variable and analysis will be carried out on the longitudinal dataset using logistic regression with a random effect for both patients and facilities, using the GLIMMIX procedure in SAS. The random effects will model the correlations among the measurements at each level. This analysis will use data from all patients, not just those with at least 60 dialysis sessions.

Dialysis facilities will be randomized in a 2x2 factorial design to two study intervention or control groups. Sample size is based on separate tests for each of the two treatment comparisons, and assumes no interaction between treatment types. The primary outcome measure is session instability, particularly IDH, which occurs in approximately 20% of hemodialysis sessions in the usual practice setting in the US. The study is powered to detect a decrease from 20% to 15-

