16% in the intervention group. It is assumed that a minimum of 60 hemodialysis patients will be observed for at least 60 dialysis sessions and the outcome will be the proportion of unstable sessions, which we treat as a continuous variable. These proportions among patients in a facility are assumed to be normally distributed with mean 0.20 in the control group and mean between 0.16 and 0.17 in the intervention group (a difference, d , of 0.034 to 0.043), with standard deviation (SD, or 'sigma') assumed to be in the range 0.08 to 0.10. We conservatively assume $n=60$ patients per facility, i.e., a total of $60 \times 20 = 1,200$ patients. The power calculation is robust to changes in number of patients (m), as the calculation of K (number of clusters) only increases by ~ 1 if m is increased to 90. The intraclass correlation coefficient for hemodialysis facilities is assumed to be 0.10. A significance level of 0.05 was assumed in all calculations. Table 5 gives the statistical power to detect a given difference (D , 0.034-0.043), with sigma values of 0.08 and 0.10, and number of clusters (dialysis units, k) per treatment group of 10 (20 facilities total).

Table 5 shows that detecting a difference of ~ 0.03 (i.e., 20% versus 17% of sessions unstable) with 80% power is only feasible with a SD (sigma) of 0.08 or less. If the standard deviation is as large as 0.10, we can detect a difference of 0.043 (i.e., 20% vs. 16%) with 81% power. Put another way, if the smallest variance estimate is correct ($\sigma=0.08$), we have 91% power to detect a 4% difference, and 80% power to detect a 3% difference.

Table 5 - The power is shown to detect a difference in IDH rates (D) between groups assuming 3 possible standard deviations (sigma). The minimum number of facilities (K) is also shown, illustrating some flexibility to accommodate drop-out. Bolded cells show power $\geq 80\%$.						
D	0.034	0.034		0.040	0.043	
Sigma	0.08	0.10		0.08	0.10	
K	10	10		10	10	
Power	80%	61%		91%	81%	

II. Secondary Outcomes

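### The factorial rationale says the trial can show the two interventions equivalent, but the named test is one of difference, no margin is set, and the five-versus-five contrast has a 95% half-width about as large as the whole assumed effect

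*Combined protocol and SAP*

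**What the plan says.** Section 4.1, part II, lists four treatment comparison questions. The third is "Comparative effectiveness of provider education alone vs. peer mentoring alone", to be answered by "Cell B vs. C – F test comparison". The text that follows argues for having a control group. It says that, with tests i and ii alongside, the trial can establish both whether an intervention beats standard care and whether it is "2) equivalent (or not) to the other intervention".

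The head-to-head is also part of the main hypothesis. Section 11.1 (and section 2.2.3) states "that multimodal provider education will show a larger improvement" and says that this hypothesis will be tested.

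Section 5.4.1 fixes the allocation as "assigning 5 facilities to each of the 4 combinations", so B versus C is 5 facilities against 5. Section 11.2 says "Sample size is based on separate tests for each of the two treatment comparisons" and gives Table 5 for a number of facilities "per treatment group of 10 (20 facilities total"). No power or precision is given for B versus C. The primary analysis in section 11.4 compares each intervention with no intervention and does not name the B−C contrast.

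**The concern.** An F test of B versus C asks whether the two cells differ. Failing to reject does not show that they are the same. An equivalence conclusion needs a margin set in advance and a rule for reading the interval against it, and the documents contain neither.

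Section 2.3.2 says the results will inform providers whether to pursue the provider-focused intervention, the patient-focused one, both or neither. If a non-significant head-to-head result were read as equivalence, that choice could rest on data that do not separate an effective intervention from an ineffective one. The plan acknowledges that it is not powered for moderate interaction effects (section 11.4). It gives no such caution for the head-to-head.

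**Working it through.** **Inputs (section 11.2 unless noted).** Patients per facility m = 60 ("a minimum of 60 hemodialysis patients will be observed for at least 60 dialysis sessions"); ICC 0.10; SD of the patient-level proportion 0.08 to 0.10; significance level 0.05. Sidedness is not stated for Table 5; two-sided is assumed here and reproduces the table. Facilities per group K = 10 for the main effects and K = 5 for B versus C (section 5.4.1).

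**Formulas.** Design effect = 1 + (60 − 1) × 0.10 = 6.9. SE = SD × √(2 × 6.9 / (K × 60)). Power (normal) ≈ Φ(D/SE − 1.96).

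**Reproducing Table 5 (K = 10).** SE = 0.01213 (SD 0.08) and 0.01517 (SD 0.10).

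| D | SD | D/SE | Power, recomputed | Table 5 |
|---|---|---|---|---|
| 0.034 | 0.08 | 2.80 | 80.0% | 80% |
| 0.034 | 0.10 | 2.24 | 61.1% | 61% |
| 0.040 | 0.08 | 3.30 | 90.9% | 91% |
| 0.043 | 0.10 | 2.84 | 80.9% | 81% |

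All four entries match under the normal approximation. With t on 18 df they would be 75.5%, 56.4%, 87.6% and 76.5%, so Table 5 used the normal distribution.

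**Does the factorial layout help?** With balanced cells, the difference between the two main effects is [(A+B) − (C+D)]/2 − [(A+C) − (B+D)]/2 = B − C. Cells A and D cancel. Tests i and ii therefore add no precision to the head-to-head, which rests on 5 versus 5 facilities.

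**B versus C (K = 5).** SE = SD × √(13.8/300) = SD × 0.2145. The t version uses 16 df (20 facilities less 4 cells).

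| | SD 0.08 | SD 0.10 |
|---|---|---|
| SE | 1.72 points | 2.14 points |
| 95% half-width, normal (1.96 × SE) | 3.36 points | 4.20 points |
| 95% half-width, t on 16 df (2.12 × SE) | 3.64 points | 4.55 points |
| Detectable with 80% power, normal (2.80 × SE) | 4.8 points | 6.0 points |
| Detectable with 80% power, t on 16 df | 5.1 points | 6.4 points |

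**Against the assumed effect.** Table 5 pairs the SDs of 0.08 and 0.10 with effects of 3.4 and 4.3 points at about 80% power. If B and C came out exactly equal, the normal interval would reach 3.36 and 4.20 points either way, just short of those effects, and the t interval would pass them. Any other non-significant estimate reaches further on one side.

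If one intervention truly had the full effect and the other none, power for B versus C would be 51% (0.034, SD 0.08) and 52% (0.043, SD 0.10) by the normal approximation, or 46% and 47% with 16 df. A non-significant result would then be about as likely as not.

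**Would adding a margin rescue the claim?** The documents give none, so these margins are illustrative. Suppose the true difference is zero, two one-sided 5% tests are used, and the margin equals the whole effect. Power = 2Φ(M/SE − 1.645) − 1 = 26% (0.034, SD 0.08) and 28% (0.043, SD 0.10). With a margin of half the effect it is about 0%. For 80% power at the whole-effect margins, about 11 facilities per cell would be needed (10.9 and 10.7).

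**Sensitivity to the ICC.** Covariate adjustment might lower it. At an assumed 0.05 the normal half-width is 2.5 to 3.2 points; at an assumed 0.02 it is 1.9 to 2.4 points.

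**The case against.** The quoted sentence belongs to an argument for a four-cell design over a two-arm trial. In that setting it reads as a loose parallel to asking whether an intervention is better than standard care. Section 11.4 contains no equivalence claim or decision rule. It makes the main effects the variables of primary interest, and section 11.2 bases the sample size on them. The plan therefore does not present B versus C as its powered comparison. All of this stands. It limits the point to a property that the rationale claims and to a missing statement of precision.

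A reader might infer three stronger things that the documents do not support:

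- *A null head-to-head will be reported as equal effectiveness.* No reporting rule says so. Section 4.1 raises equal effectiveness only in a hypothetical about a two-arm trial.
- *The detectable B−C difference exceeds every effect the plan assumes.* Section 11.2 also says the study is powered for a fall from 20% to 15–16%, which is 4 to 5 points. The 4.8 points at SD 0.08 (normal) lies inside that range.
- *The power for some particular small provider-versus-patient difference can be read from the plan.* It cannot. The 0.034 and 0.043 in Table 5 are alternative effects for the same intervention-versus-control comparison, not expected effects of two different interventions.

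**Conclusion.** The claim is wrong as written. The design rationale credits the trial with being able to establish equivalence, but it names only a test of difference and sets no margin. On the plan's inputs the head-to-head has a 95% half-width of 3.4 to 4.2 points (3.6 to 4.5 with 16 df). That is about the whole Table 5 effect; the full interval is twice as wide. The difference detectable with 80% power is 4.8 to 6.0 points (5.1 to 6.4 with 16 df).

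These sizes rest on an ICC of 0.10 before covariate adjustment, 60 patients in each facility, and SDs of 0.08 to 0.10. A lower ICC would narrow the interval, but a non-significant F test would still not show equivalence. The provider-is-better half of the main hypothesis rests on this same contrast and is not covered by Table 5. The tests of each intervention's main effect are not affected.

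**What to change.** In section 4.1, part II, replace the equivalence wording with something like *different (or not) from the other intervention*. Add that a non-significant B versus C result is inconclusive and is not evidence of equivalence.

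In section 11:

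- Name the B−C contrast and say that it will be reported as an estimate with its 95% confidence interval.
- State its expected half-width and its detectable difference on one named reference distribution: 3.4 to 4.2 and 4.8 to 6.0 points by the normal approximation of Table 5, or 3.6 to 4.5 and 5.1 to 6.4 points with t on 16 df.
- Note that the larger-improvement part of the main hypothesis depends on this contrast and that the Table 5 power does not apply to it.

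The cost is a few sentences and a more modest claim. Design, data collection and the main-effect analyses stay as they are. Relabelling that half of the hypothesis as secondary would change its status, not just its wording, and this correction does not require it.
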